8.4.7.1. Hepatitis B Monitoring

Subjects whose results are HBcAb positive at screening, regardless of hepatitis B surface antibody (HBsAb) status, will have an HBV DNA test performed by the central laboratory. Subjects whose results are found to be HBV DNA positive (detectable) at screening will be excluded from the trial. Subjects whose results are HBV DNA negative (undetectable) may be enrolled into the study, according to investigator judgment, with HBV DNA monitoring approximately every 4 weeks during treatment as detailed in the Schedule of Activities ([Appendix 2](#)). Subjects participating in Part B who are positive for HBcAb will continue to have HBV DNA monitoring every 3 months (for 6 months) after the last dose of study drug. Once

subjects test positive for HBV DNA, they should be managed as clinically indicated and discontinued from the study (HBV monitoring is no longer required within the study at that point).

Subjects whose results are HBcAb negative and HBsAb positive will not require testing for HBV DNA because they are likely to have been vaccinated for HBV and have a very low risk of reactivation. These subjects will be followed up by routine liver tests as part of the monitoring process.

If the result of the HBV DNA testing is positive at any time after screening, the subject must discontinue the study drug and should receive appropriate follow-up medical care, including consideration for antiviral therapy. A specialist physician in the care of patients with hepatitis (for example, infectious disease physician or hepatologist) should be consulted. The timing of discontinuation from the study drug and any other immunosuppressant therapy should be based on the recommendations of the consulting specialist physician in conjunction with the investigator and medical guidelines/standard of care.

8.5. Pharmacokinetics

At the visits and times specified in the Schedule of Activities ([Appendix 2](#)), venous blood samples of approximately 4 mL each will be collected to determine the plasma concentrations of LY3337641. At the baseline visit (Visit 2 in Part A and Visit 102 in Part B), the first dose of study drug will be administered, and subjects will remain at the site and have the PK sample drawn between 30 minutes and 2 hours postdose. At subsequent visits, the PK sample will be drawn at any time during the visit; it is not required that the dose be administered during the visit.

A maximum of 2 PK samples may be drawn at additional time points during the study if warranted and agreed upon between both the investigator and sponsor. For example, if an SAE or a clinically significant rash is observed by the investigator and a PK sample is not scheduled for that visit, a sample may be drawn at that time.

Instructions for the collection and handling of blood samples will be provided by the sponsor. The actual date and time (24-hour clock time) of each sampling will be recorded. It is essential that the actual times of dosing and sampling are recorded accurately.

Drug concentration information that may unblind the study will not be reported to investigative sites or personnel who are blinded to study data.

Plasma samples will be analyzed for LY3337641 at a laboratory approved by the sponsor using validated liquid chromatography-tandem mass spectrometry methodology. Analysis of samples collected from placebo-treated subjects is not planned.

Plasma PK samples may be analyzed for exploratory metabolite identification, as deemed appropriate by the sponsor. The results of such exploratory metabolism work may only be included in the clinical study report (CSR) if deemed appropriate by the sponsor or may be reported in a separate exploratory metabolism report.

Bioanalytical samples collected to measure LY3337641 concentration will be retained for a maximum of 1 year following the last subject visit for the study.

8.6. Pharmacodynamics

At the visits and times specified in the Schedule of Activities ([Appendix 2](#)), venous blood samples will be collected for the analysis of PD endpoints. Pharmacodynamic endpoints that are planned to be measured include total Ig, IgG, IgM, and IgA (Part B only). Additionally, BTK occupancy and phosphorylated BTK will be assessed and samples will be drawn only at sites that meet assay requirements.

Bioanalytical samples collected to measure PD endpoints will be identified by the subject number (coded) and retained for a maximum of 1 year following last subject visit for the study at a facility selected by the sponsor.

8.7. Genetics

A blood sample will be collected for pharmacogenetic analysis as specified in the Schedule of Activities ([Appendix 2](#)) where local regulations and ERBs allow.

Samples will not be used to conduct unspecified disease or population genetic research either now or in the future. Samples will be used to investigate variable response to LY3337641 and to investigate genetic variants thought to play a role in RA. Assessment of variable response may include evaluation of AEs or differences in efficacy. These studies may include but are not limited to genetic variants thought to play a role in RA and genes that play a role in leukocyte (B-cell receptor, Fc receptor, or T-cell receptor) signaling pathways to evaluate their association with observed response to LY3337641.

All pharmacogenetic samples will be coded with the subject number. These samples and any data generated can be linked back to the subject only by the investigator site personnel. Samples will be destroyed according to a process consistent with local regulations.

Samples will be retained for a maximum of 15 years after the last subject visit for the study, or for a shorter period if local regulations and/or ERBs impose shorter time limits, at a facility selected by the sponsor. This retention period enables use of new technologies, response to regulatory questions, and investigation of variable response that may not be observed until later in drug development or when the drug is commercially available.

Molecular technologies are expected to improve during the 15-year storage period and therefore cannot be specifically named. However, existing approaches include whole genome or exome sequencing, genome-wide association studies, candidate gene studies, and epigenetic analyses. Regardless of the technology utilized, genotyping data generated will be used only for the specific research scope described here.

8.8. Biomarkers

Serum, plasma, and whole blood samples for nongenetic biomarker research will be collected at the times specified in the Schedule of Activities ([Appendix 2](#)) where local regulations and ERBs allow.

Samples will be used for research on the drug target, disease process, pathways associated with RA, mechanism of action of LY3337641, and/or research method or in validating diagnostic tools or assay(s) related to RA. Proteomic, gene-expression, genomic, epigenetic, or metabolomic analyses may be performed on these samples.

All biomarker samples will be coded with the subject number. These samples and any data generated can be linked back to the subject only by the investigator site personnel. Samples will be destroyed according to a process consistent with local regulations.

Samples will be retained for a maximum 15 years after the last subject visit for the study, or for a shorter period if local regulations and ERBs impose shorter time limits, at a facility selected by the sponsor. This retention period enables use of new technologies, response to regulatory questions, and investigation of variable response that may not be observed until later in drug development or when the drug is commercially available.

8.9. Health Outcomes

Health outcomes measures should be administered according to the Schedule of Activities ([Appendix 2](#)) in countries where the questionnaires have been translated into the native language of the region and linguistically validated.

The health outcomes measures to be assessed in this study are described in the following subsections (refer to Section [8.1.1](#) for health outcomes measures included in the ACR20 efficacy assessment).

- Medical Outcomes Study 36-Item Short Form Health Survey (SF-36) (only in Part B)
- Functional Assessment of Chronic Illness Therapy–Fatigue (FACIT-F) (only in Part B)
- morning joint stiffness duration
- patient’s assessment of sexual function (VAS) (only in Part B).

Any measures that are subject self-assessments should be completed *before* the study visit examinations.

8.9.1. SF-36

The SF-36v2 Acute measure (SF-36) is a subjective, generic, health-related quality of life instrument that is patient-reported and consists of 36 questions covering 8 health domains: physical functioning, bodily pain, role limitations due to physical problems, role limitations due to emotional problems, general health perceptions, mental health, social function, and vitality. Each domain is scored by summing the individual items and transforming the scores into a 0 to 100 scale with higher scores indicating better health status or functioning. In addition, 2 summary scores, the PCS (physical component score) and the MCS (mental component score),

will be evaluated based on the 8 SF-36v2 Acute domains (Brazier et al. 1992; Ware and Sherbourne 1992).

8.9.2. FACIT-F

The FACIT-F scale (Cella and Webster 1997) is a brief, 13-item, symptom-specific questionnaire that specifically assesses the self-reported severity of fatigue and its impact upon daily activities and functioning. The FACIT-F uses 0 (“not at all”) to 4 (“very much”) numeric rating scales to assess fatigue and its impact in the past 7 days. Scores range from 0 to 52 with higher scores indicating less fatigue.

8.9.3. Morning Joint Stiffness Duration

Subjects will be asked by site personnel to assess their duration of morning joint stiffness on the day prior to the visit. Responses will be recorded in minutes.

8.9.4. Patient’s Assessment of Sexual Function (VAS)

Subjects will be asked to assess the extent of the effect that RA has had on their sexual activity over the past week by using a 100-mm horizontal VAS where the left end represents “no effect on my sexual activity” and the right end represents “completely stopped my sexual activity.”

9. Statistical Considerations and Data Analysis

9.1. Determination of Sample Size

Approximately 32 at least mildly active RA subjects will be enrolled and randomly assigned in a 1:1:1:1 ratio to 1 of the 3 doses of LY3337641 (5, 10, or 30 mg) or placebo in Part A. This sample size is customary for evaluating safety and PK and/or PD parameters, and is not powered on the basis of statistical hypothesis testing.

Approximately 244 moderately to severely active RA subjects will be enrolled and randomly assigned in a 1:1:1:1 ratio to 1 of the 3 doses of LY3337641 (5, 10, or 30 mg) or placebo in Part B. All subjects who discontinue the treatment early (before Week 12) will be considered as failing the primary endpoint in Part B. The sample size of 61 subjects per arm will provide at least 80% power at the 2-sided .05 significance level to detect a difference of 25% in the primary endpoint (ACR20 response rate at Week 12) between each LY3337641 dose and placebo, assuming a 30% placebo response rate.

If the Assessment Committee determines that a dose adjustment is needed (Section 6.6), the total study sample size may be adjusted.

9.2. General Statistical Considerations

Statistical analysis of this study will be the responsibility of Eli Lilly and Company or its designee.

In general, continuous variables will be summarized including number of observations; mean; standard deviation; and minimum, median, and maximum values. Categorical variables will be presented as counts and percentages. Data from Part A will be summarized separately from data from Part B. No statistical hypothesis testing is planned for Part A. All tests of treatment effects in Part B will be conducted at the 2-sided α level of .05, unless otherwise stated. No adjustments for multiplicity will be performed.

Complete details of the planned analyses will be documented in the statistical analysis plan (SAP). Any change to the data analysis methods described in the protocol will require an amendment ONLY if it changes a principal feature of the protocol. Any other change to the data analysis methods described in the protocol and the justification for making the change will be described in the CSR. Additional exploratory analyses of the data will be conducted as deemed appropriate.

9.2.1. Analysis Population

Unless otherwise specified, efficacy and health outcomes analyses will be conducted on the modified intent-to-treat population, defined as all randomized subjects receiving at least 1 dose of study drug. The analysis population (for applicable treatment outcome measures) will be all subjects with both a baseline and at least 1 postbaseline data measurement. Subjects will be grouped according to the randomized treatment. In addition, the primary analysis of Part B will be repeated using the per-protocol set, defined as all subjects randomly assigned to the study drug and using the study drug for 12 weeks.

Safety analyses will be conducted on the safety population, defined as all randomized subjects receiving at least 1 dose of the study drug. Subjects will be grouped according to the randomized treatment.

9.2.2. Baseline Definition

The baseline will be defined as the last available value before the first administration of study drug for both efficacy and safety analyses, including unscheduled measurements for both parts separately. In most cases, this will be the measure recorded on Study Day 1 (Visit 2 in Part A, Visit 102 in Part B). Change from baseline values will be calculated as the postbaseline value minus the baseline value for each scheduled postbaseline time point. If the baseline value is missing (ie, no screening values, no Day 1 value, and no unscheduled measurements), the change from baseline will be missing as well.

9.2.3. Missing Data Imputation

The methods for imputation of missing data will be outlined in the SAP.

9.3. Treatment Group Comparability

9.3.1. Subject Disposition

A detailed description of subject disposition will be provided. Details will be outlined in the SAP.

9.3.2. Subject Characteristics

The subject's sex, weight, height, and other demographic characteristics will be recorded. Details will be outlined in the SAP.

9.3.3. Concomitant Therapy

Details will be outlined in the SAP.

9.3.4. Treatment Compliance

Treatment compliance will be evaluated by visit and overall during the study. Details will be provided in the SAP.

9.4. Primary and Secondary Analyses

9.4.1. Primary Analyses

The primary objective in Part A is safety (Section 9.5).

The primary endpoint in Part B will be analyzed by a logistic regression model with ACR20 at Week 12 as the dependent variable and treatment, biologic DMARD experience (yes/no), region (Japan vs non-Japan), and baseline DAS28-hsCRP as independent variables. The comparison of each LY3337641 dose to placebo will be presented. Subjects who discontinue from the study earlier than Week 12 and subjects who complete 12 weeks of dosing but do not have sufficient

data to derive the ACR20 response (Section 8.1.1) will be considered as failing to meet the ACR20.

9.4.1.1. Additional Analyses of the Primary Efficacy Measure

The number and percentage of subjects achieving the ACR20 response over time in both parts will be summarized separately by treatment group. All subjects who discontinue study drug at any time for any reason will be defined as nonresponders from time of discontinuation forward for ACR analyses.

The ACR20 will also be analyzed using the per-protocol set (Section 9.2.1) as a sensitivity analysis in Part B. Details will be outlined in the SAP.

Each component of the ACR20 (ie, TJC, SJC, Physician's Global Assessment of Disease Activity, Patient's Global Assessment of Disease Activity, pain score, HAQ-DI, and hsCRP) in both parts will be summarized separately over time by treatment. The change from baseline to postbaseline in Part B will be analyzed by a maximum-likelihood-based mixed model repeated measures (MMRM) analysis of covariance. The change from baseline for each component of the ACR20 to each postbaseline time point in Part B is the dependent variable in the model.

Baseline, treatment, weeks of treatment (categorical), the interaction of treatment and weeks, biologic DMARD experience (yes/no), region (Japan vs non-Japan), and baseline DAS28-hsCRP are fixed effects; subjects and error are random effects.

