9.4.2. Secondary Analyses

ACR50 and ACR70 will be summarized for both parts separately. Data from Part B will be analyzed using methods similar to those for the primary analysis.

DAS28-hsCRP will be summarized separately for each part by treatment and each postbaseline visit. Change from baseline in DAS28-hsCRP to each postbaseline time point in Part B will be analyzed by the MMRM approach. Subjects with DAS28-hsCRP <2.6 will be considered as having achieved clinical remission; the criterion for achieving LDA will be DAS28-hsCRP \leq 3.2. The number and percentage of subjects who achieve clinical remission or LDA will be summarized separately and analyzed using methods similar to those for the primary analysis.

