Subjects will be randomly assigned at baseline (Visit 102) in a 1:1:1:1 ratio to 1 of 4 arms: 3 experimental arms in which LY3337641 will be dosed orally at 5, 10, or 30 mg and 1 placebo comparator arm. Study drug will be administered qd in a blinded fashion from Week 0 through Week 12. Five clinic visits are planned during this period (Visits 102 to 106) at Weeks 0, 2, 4, 8, and 12. At these visits, subjects will undergo safety evaluations, clinical assessments, PK samplings, and other laboratory assessments according to the Schedule of Activities table.

Safety Follow-Up Period (Visit 802, Week 14, Study Day 99)

All subjects will have a safety visit (Visit 802) at least 2 weeks after the final dose of study drug. For subjects who discontinue the study early, an additional safety visit is only required if the EDV occurs less than 2 weeks after the last dose of study drug.

Additional HBV DNA Monitoring (Visits 803 and 804, Study Days 169 to 253)

HBV DNA will be monitored every 3 months (for 6 months) after the last dose of study drug for those subjects who are HBcAb+ and HBV DNA negative (undetectable) at screening.

Schedule of Activities, Protocol I8K-MC-JPDA – Part A

Perform procedures as indicated.

	Screening	Baseline (Random- ization)	Dosing Period			Safety Follow-Up	Comments
	V1	V2	V3	V4	V5 & EDV	V801 ^a	
eCRF Visit Number (V)	V1	V2	V3	V4	V5 & EDV	V801 ^a	
Study Day (\pm day(s))	≤ 28 Days from V2	1	8 ± 3	15 ± 3	29 ± 3	43 +7	
Study Week		0	1	2	4	6	
Informed consent	X						Must be completed prior to performing any study-related procedures or tests.
Review and confirm inclusion/exclusion criteria	X	X					
Complete medical history, pre-existing conditions	X						
Complete physical exam	X						
Symptom-directed physical exam (as clinically indicated)		X	X	X	X	X	Symptom-directed physical examinations are not required at each visit but may be conducted at the investigator's discretion at any visit and any time a subject presents with complaints.
Adverse events	X	X	X	X	X	X	AEs will be graded as mild/moderate/severe except rash, which will use CTCAE grading.
Concomitant drugs	X	X	X	X	X	X	
Height	X						Subject should remove shoes.
Body weight	X	X			X		
Vital signs	X	X	X	X	X	X	Vital signs include heart rate and blood pressure.
Temperature	X						May be repeated as clinically indicated.
ECG	X						A local ECG will be collected at screening and may be repeated at the investigator's discretion at any visit.

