6.1. General Statistical Considerations

Statistical analysis of this study will be the responsibility of Eli Lilly and Company or its designee.

This plan describes a priori statistical analyses for safety, efficacy, and health outcomes data that will be performed.

In general, continuous variables will be summarized including number of observations, mean, standard deviation (SD), minimum, median, and maximum values. Categorical variables will be presented as counts and percentages. Data from Part A will be summarized separately from data from Part B. No statistical hypothesis testing is planned for Part A. All tests of treatment effects in Part B will be conducted at the 2-sided α level of .05, unless otherwise stated. No adjustments for multiplicity will be performed.

Unless otherwise specified, statistical analyses to compare treatment groups will use statistical techniques with treatment group and randomization strata [ie, biologic DMARD experience (yes/no), region (Japan versus non-Japan), and baseline DAS28-hsCRP (continuous)] as factors. In addition, for analysis of continuous measures, the baseline value of the dependent variable will be included as a covariate. Fisher's exact test will be used for the analysis of categorical measures unless otherwise specified.

P-values from statistical tests of treatment effects in safety analyses should be interpreted with caution as the analyses are intended to be descriptive and should not be considered as formal hypothesis testing. P-values and confidence intervals (CIs), if reported, provide some evidence of the strength of the finding.

For the purpose of presentation, the treatment groups of Parts A and B will be assigned by randomized treatment, and the treatment groups of Follow-up period will be assigned by the last used treatment.

The analyses for the optional long-term extension is described in Section [6.5.5](#).

Additional exploratory analyses of the data will be conducted as deemed appropriate.

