6.3.2. Additional Analyses on the Primary Efficacy Measure

The ACR20 in Part A will be derived using ACR core set components and follow the algorithm in Section 6.3.1. Each component of the ACR20 (ie, TJC, SJC, Physician’s Global Assessment of Disease Activity, Patient’s Global Assessment of Disease Activity, patient’s assessment of pain, HAQ-DI, and hsCRP) and ACR20 in Part A will be summarized over time by treatment.

The primary endpoint in Part B will also be analyzed by a logistic regression model with ACR20 at Week 12 as the dependent variable and treatment, region (Japan versus non-Japan), biologic DMARD experience (yes/no), and baseline DAS28-hsCRP as independent variables using the per-protocol population as a sensitivity analysis. Each component of the ACR20 (ie, TJC, SJC, Physician’s Global Assessment of Disease Activity, Patient’s Global Assessment of Disease Activity, patient’s assessment of pain, HAQ-DI, and hsCRP) will be summarized over time by treatment. The change from baseline will be analyzed by a maximum-likelihood-based mixed model repeated measures (MMRM) analysis of covariance (ANCOVA). The change from baseline for each component of the ACR20 to each scheduled postbaseline time point is the dependent variable in the model. Baseline, treatment, region (Japan versus non-Japan), week of treatment (categorical), the interaction of treatment and week, biologic DMARD experience (yes/no), and baseline DAS28-hsCRP are fixed effects; subject and error are random effects. The covariance structures to be tested in this model include unstructured covariance, compound symmetry (CS), heterogeneous CS, heterogeneous autoregressive (AR1), or heterogeneous Toeplitz. The best covariance structure will be selected based on the Akaike’s Information Criterion (AIC). The Kenward-Roger approximation will be used to estimate the denominator degrees of freedom. Type III tests for the least squares mean (LSMean) will be used for the statistical comparison; the 95% CI will also be reported.

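### The repeated-measures models give baseline one slope for all weeks, so if that slope changes over time the Week 12 contrasts for DAS28-hsCRP and the ACR components can be somewhat less precise than the collected data allow

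*Protocol*

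**What the plan says.** The Part B models for change from baseline are described in both documents.

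- **ACR components.** Protocol 9.4.1.1 gives the fixed effects as "Baseline, treatment, weeks of treatment (categorical), the interaction of treatment and weeks, biologic DMARD experience (yes/no), region (Japan vs non-Japan), and baseline DAS28-hsCRP". SAP 6.3.2 has the same terms in another order: "Baseline, treatment, region (Japan versus non-Japan), week of treatment (categorical), the interaction of treatment and week, biologic DMARD experience (yes/no), and baseline DAS28-hsCRP".
- **DAS28-hsCRP.** Protocol 9.4.2 says "Change from baseline in DAS28-hsCRP to each postbaseline time point in Part B will be analyzed by the MMRM approach". SAP 6.3.3.2 writes out the list, which is the same as for the components. Here the general baseline term and baseline DAS28-hsCRP are one and the same variable.
- **Patient-reported outcomes.** SAP 6.3.4.2 (sexual function), 6.3.4.3 (SF-36) and 6.3.4.4 (FACIT-F) repeat the list.
- **General rule.** SAP 6.1 says that "for analysis of continuous measures, the baseline value of the dependent variable will be included as a covariate". It does not say whether the slope may vary by visit.
- **Covariance.** SAP 6.3.2 names five candidates, from unstructured to compound symmetry, and chooses by AIC: "The best covariance structure will be selected based on the" Akaike criterion.
- **Visits.** Protocol Appendix 2: "Five clinic visits are planned during this period (Visits 102 to 106) at Weeks 0, 2, 4, 8, and 12". Four of these are postbaseline.

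Neither document contains a baseline-by-week term.

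**The concern.** With a main effect only, the model uses one baseline slope at every visit. For a change score there is reason to expect the slope to move. If a subject's correlation with baseline fades over time, or if improvement is roughly proportional to the starting level and accumulates, the slope of change on baseline steepens from Week 2 to Week 12. A common slope is then a compromise. Under an unstructured covariance it can sit nearer the early visits. Baseline would be under-adjusted at Week 12, the visit named in the secondary objective, and variance that the recorded baseline could remove would stay in the contrast. What is at stake is interval width for one secondary endpoint and several exploratory ones.

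**Working it through.** **1. The plan's own figure.** The only power statement is for ACR20: "The sample size of 61 subjects per arm will provide at least 80% power at the 2-sided .05 significance level to detect" a 25-point difference from a 30% placebo rate (Protocol 9.1). With p1 = 0.30, p2 = 0.55 and mean 0.425:

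n = [1.96 x sqrt(2 x 0.425 x 0.575) + 0.842 x sqrt(0.30 x 0.70 + 0.55 x 0.45)]^2 / 0.25^2 = (1.370 + 0.569)^2 / 0.0625, about 60.2, so 61 per arm.

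Power at 61 is 80.5% (pooled variance). The figure reproduces. It belongs to a single-visit logistic regression and does not involve the MMRM.

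**2. Formula for the loss.** With treatment-by-week in the model and complete data, the Week 12 contrast is the difference in mean change minus b times the difference in mean baseline. Let beta_t be the true slope at week t, and b the generalised least squares common slope, b = (1'V^-1 beta) / (1'V^-1 1). Then

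variance ratio (common / by-week) = 1 + (beta_12 - b)^2 x var(baseline) / residual variance at Week 12.

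The ratio cannot fall below 1 for a given covariance structure. It equals 1 when the slope is constant.

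**3. Scenarios by baseline correlation.** The documents give no SDs or correlations, so all inputs are assumed: baseline SD 1, correlation between adjacent visits 0.75, and beta_t = r_t x s_t - 1, where r_t is the correlation with baseline and s_t the SD at week t.

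| Correlation with baseline, Week 2 to 12 | SD by visit | Ratio, unstructured | Ratio, compound symmetry |
|---|---|---|---|
| 0.50 constant | 1.2 | 1.000 | 1.000 |
| 0.60 to 0.45 | 1.10 to 1.25 | 1.003 | 1.002 |
| 0.60 to 0.45 | 1 | 1.009 | 1.007 |
| 0.70 to 0.40 | 1.1 to 1.4 | 1.017 | 1.008 |
| 0.70 to 0.40 | 1 | 1.046 | 1.027 |
| 0.80 to 0.30 | 1 | 1.185 | 1.076 |
| 0.80 to 0.20 | 1 | 1.288 | 1.094 |

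Worked row (0.70 to 0.40, SD 1, unstructured): beta_12 = -0.60, b = -0.404, residual variance 1 - 0.40^2 = 0.84, so the ratio is 1 + 0.196^2 / 0.84 = 1.046. The first five rows are the basis for 0-5% on DAS28-hsCRP. That is at most about 2.5% of the standard error, since sqrt(1.05) = 1.025. A steeper fall in correlation would exceed this range.

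**4. Joint counts.** A second model treats the Week t count as true baseline times a share remaining. Assumed inputs: baseline mean/SD 24/13 or 16/9; mean share 85/72/58/50% or 90/80/70/65% at Weeks 2/4/8/12; between-subject SD of the share 0.3-0.5 at Week 12; 400,000 simulated subjects per scenario.

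- Baseline without error, unstructured covariance: Week 12 residual variance about 5-33% higher. For example, with mean/SD 24/13, share 50%, share SD 0.3, Week 12 slope -0.50 and common slope about -0.15, the excess is 0.35^2 x 13^2 / [0.3^2 x (24^2 + 13^2)] = 20.7 / 67.1, about 31%.
- Baseline reliability 0.65-0.8: about 1-5%.
- Visits weighted equally, as under compound symmetry: about 0.3-7%.

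The error-free figure also depends on the assumed correlation of the share between visits. At 0.8 between adjacent visits it was 7-41%, against 2-6% at reliability 0.8.

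**5. Bias check.** Four arms of 61 were simulated with no treatment effect, 400 replicates per scenario, with an unstructured fit. The mean Week 12 difference was at most 0.022 in absolute value, against a standard error of about 0.2, and nearly equal under both models. Standard-error ratios were 1.000, 1.001, 1.022 and 1.088 for correlations constant at 0.50, 0.60 to 0.45, 0.70 to 0.40 and 0.80 to 0.30. With about 15% dropout they were 1.000, 1.001, 1.022 and 1.090.

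**The case against.** The case for leaving the model alone is a fair one. A main-effect baseline follows the SAP's own covariate rule, the comparison stays randomised, and nothing in the documents shows that the slope varies. The larger joint-count figures need a baseline with almost no measurement error. Joint counts are assessor ratings, and Part B requires at least 6 swollen and 6 tender joints at screening. Regression to the mean therefore already produces a negative slope at Week 2, which narrows the spread between weeks. The figures also need a covariance that favours the early visits, and the AIC step may choose otherwise. All of this stands, and it limits the size. It does not remove the point, because in large samples week-specific slopes cannot lose Week 12 precision under the same covariance structure.

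A reader might go further in three ways that the documents do not support.

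- *That the Week 12 contrasts are certainly less precise.* The loss is zero if the slope is constant, and the documents do not settle whether it is.
- *That the trial falls below its stated 80% power.* That figure is for ACR20 only. No power or precision target is stated for any MMRM endpoint.
- *That the repeated baseline in the DAS28-hsCRP model distorts the result.* A duplicate column is redundant and leaves the treatment contrasts unchanged.

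**Conclusion.** The point holds as a modest, conditional matter of efficiency. Each MMRM with a baseline term holds its slope fixed over Weeks 2 to 12. If the true slope varies, Week 12 precision is lost although the data to recover it are already collected.

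The size rests wholly on assumed SDs, correlations and reliabilities. For DAS28-hsCRP change, about 0-5% of Week 12 residual variance is a reasonable range when the correlation with baseline is constant or falls moderately. For the exploratory joint counts, about 1-5% is reasonable with realistic baseline error. Losses of 20% or more there need near error-free baselines together with an unstructured covariance. No bias arises, and neither the primary ACR20 analysis nor the sample size is touched.

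**What to change.** In the SAP, add a baseline-by-week interaction to the fixed effects in 6.3.2, 6.3.3.2, 6.3.4.2, 6.3.4.3 and 6.3.4.4. In 6.3.3.2, list baseline DAS28-hsCRP once, with its by-week interaction. Removing the duplicate is a tidy-up and does not itself change the estimates.

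The cost is 3 extra parameters per model (4 postbaseline visits minus 1) with about 244 subjects, and no new data or visits. Protocol 9.2 asks for an amendment only when a principal feature changes, and otherwise for the change to be justified in the study report. SAP wording with a note in the report should therefore be enough.
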